1.0 PROTOCOL 1 HYPOTHESES AND ENDPOINTS

1.0.1 Objectives:

The purpose of this study is to determine the effect of reducing total dietary and saturated fat intake on plasma lipids and lipoproteins, and on hemostatic factors. The study will be carried out in healthy male and female, white and black adults. In particular, we are interested in determining if further reductions in total and saturated fat, beyond the levels recommended in the Step 1 diet, are efficacious in these gender and ethnic specific groups.

1.0.2 Specific Aims:

1. To compare the effects of three diets, differing in total and saturated fat content, on plasma lipids and lipoproteins in healthy adults.
2. To compare the effects of these diets on plasma hemostatic factors in healthy adults.
3. To determine if males and females, and individuals with different ethnic origins respond to these diets.
4. To evaluate the role of the menstrual cycle in modulating diet responses in females.

1.0.3 Study Outcomes:

1. The primary lipid and lipoprotein endpoints will be plasma concentrations of total cholesterol and triglycerides, low density lipoprotein (LDL) cholesterol, high density lipoprotein (HDL) cholesterol, apoprotein B, apoprotein A-I, and lipoprotein (a). In addition, we will determine the apoE genotype of each participant.
2. The primary hemostatic endpoints will be plasma levels of fibrinogen, Factor VII and Plasminogen Activator Inhibitor I (PAI-1).
3. Several ancillary studies will be carried out to study a variety of secondary endpoints.

1.0.4 Rationale for endpoints:

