8. PAI-1

Plasminogen activator inhibitor-1 (PAI-1), a major plasma regulator of fibrinolysis, is associated with plasma lipids, especially triglycerides, and has been shown to be elevated in those with prevalent CVD. It is also elevated in those who go on to have a second myocardial infarction compared to those who do not. Other than that, there are no prospective data concerning PAI-1, but several studies are ongoing at the present time. PAI-1 is elevated in diabetics and some have proposed that this is due directly to plasma insulin. However, clinical studies have failed to reveal an acute response to insulin, so the insulin connection is currently in question. A second candidate is the plasma triglyceride level, since this is responsive to insulin to a certain extent, and might provide the link to insulin seen cross-sectionally. Since there is little known about the influence of diet on PAI-1, the studies proposed here may shed some light on this issue. PAI-1 levels appear to have a diurnal cycle, requiring the collection of samples between 7 and 10 a.m.

9. Baseline chemistry and TSH

Liver function tests (AST, ALT), renal profile (BUN, creatinine), glucose, and thyroid stimulating hormone (TSH) are performed at baseline to identify individuals with conditions which could modify dietary responsiveness to fats and cholesterol. Individuals who have these conditions should not participate in the study for both scientific and safety reasons.

10. Hematology

Hematocrit, hemoglobin, and white blood cell count should be monitored at baseline to assure that the subject will not suffer untoward effects from serial phlebotomy.

11. Other analytes considered

Additional analytes considered include glucose and insulin, platelet factor 4, and beta thromboglobulin, and a number of other coagulation parameters. For Study I, it was decided that the protocol for laboratory analyses would be rather simple. However, a large number of aliquots of serum plasma and buffy-coat cells will be carefully stored, to allow later analyses. Similarly, 24-hour urine collections will be of interest, but are put off to later studies, especially those which have fats which may affect prostaglandin metabolism.

II. BLOOD COLLECTION -- AN OVERVIEW

A. Overview

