The DELTA Study requires collection of approximately 25.5 ml of blood from participants at baseline and approximately 36 ml of blood four times at the end of each diet phase. Additional samples may be required from premenopausal women. Since the study depends on the voluntary participation of subjects, both initially and in follow-up, every effort must be made to make the entire procedure as easy and painless as possible, both for the participants and for the field center personnel.

The following schematic describes the blood sampling for a single study subject (Figure 1).

The LDX Capillary Blood Analyzer by Cholestech Corporation (Walnut Creek, CA) will be used for subject screening. This instrument provides accurate and rapid (three minute) results for total and HDL cholesterol and triglycerides (if fasting) at reasonable cost. The Cholestech Corporation has agreed to donate one machine per field center and 500 cassettes at cost for this project. Publications which describe subject screenings should acknowledge use of this instrument in the Methods section and the contribution of Cholestech Corporation in the Acknowledgements. Technicians using this instrument should receive training by OSHA regulations, sample collection technique, and the proper use of this equipment.

Recruitment

Capillary Blood Total and HDL

Baseline	Baseline Package
Diet A, Week 5,6,7,8	Four endpoint packages
Diet B, Week 13,14,15,16	Four endpoint packages
Diet C, Week 21,22,23,24	Four endpoint packages

The baseline package contains serum for a chemistry profile and TSH (6 ml), EDTA plasma for hematology (3.5 ml), EDTA - plasma for buffy-coat (10 ml), and serum for a fasting lipoprotein profile (6 ml) for a total of 25.5 ml of whole blood.

The endpoint package contains a serum for lipid profile, apolipoproteins, and aliquots (9.5 ml), a tube for serum aliquots (9.5 ml), a citrate-plasma tube at room temperature (4.5 ml) for Factor VII, a second citrate-plasma tube at 4°C (4.5 ml) for fibrinogen and PAI-1, and an EDTA-plasma tube at 4°C (7.0 ml) for a total of 35 ml. For the endpoint package, any participants who are concerned about the volume of blood should be reassured that the total amount of blood is 1/15th of the volume given in a typical Red Cross blood collection (450 ml). Each endpoint package should be collected after an 8-hour fast with sample collection occurring between 7-10 a.m.

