Serum was selected for analysis of lipoproteins inspite of the fact that many large studies have used plasma in the past. The reasons for this are severalfold. First, the EDTA used as anticoagulant extracts water from red cells, diluting the plasma somewhat. This problem translates into increased variability, since this process seems variable from person to person.

FIGURE 1: SCHEDULE OF CLINICAL LABORATORY MEASUREMENTS IN STUDY I

Measure	Type	Minimum Whole Blood Volume (ml)	Screening	Baseline	Week and Diet Endpoints		
					A 5,6,7,8	B 5,6,7,8	C 5,6,7,8
Total Cholesterol	Capillary	0.05	x				
Chemistry Hematology	Serum	6.0		x			
	EDTA Plasma	4.0		x			
Lipid Profile	Serum	6.0		x			
Apo E Phenotype	EDTA Plasma	10.0		x			
Lipid Profile Apoproteins A-1,B Lp(a)	Serum	10.0			x,x,x,x	x,x,x,x	x,x,x,x
Fibrinogen PAI-1	Citrate Plasma	4.5			x,x,x,x	x,x,x,x	x,x,x,x
Factor VII	Citrate Plasma	4.5			x,x,x,x	x,x,x,x	x,x,x,x
Aliquots for Ancillary Studies	Serum	10.0			x,x,x,x	x,x,x,x	x,x,x,x
Aliquots for Ancillary Studies	EDTA Plasma	7.0			x,x,x,x	x,x,x,x	x,x,x,x

FIGURE 2: SAMPLE PROCESSING FOR STUDY I

	BASELINE					ENDPOINT				
	1	2	3	4		1	2	3	4	5
VOLUME (ml)	Red 6	Red 6	Purple 4	Purple 10		Yellow/ Black 10	Blue 4.5	Blue 4.5	Purple 7.0	Yellow/ Black 10
IMMEDIATE TEMPERATURE	RT	RT	RT	RT		RT	RT	4°	4°	RT
Stage 1 Centrifugation (0-20 min)				Centrifuge RT 1500 g x 10 min		Centrifuge 4°C 3000 g x 10 min	Centrifuge RT 3000 g x 10 min	Centrifuge 4°C 3000 g x 10 min	Centrifuge 4°C 3000 g x 10 min	Centrifuge 4°C 3000 g x 10 min
Stage 2 Aliquot (10 min)				Buffy Coats (3x.5 ml ampules) Amber		7 Cryovial Red	4 Cryovial Green	4 Cryovial Blue	6 Cryovial Lavender	7 Cryovial Red
Stage 3 Freeze		x				x	x	x	x	x
Ship	Clin Chem	Field Lipid Lab	Clin Hem	Central Lipid Lab (1 Amber)		Field and Central Lipid Labs (4 Red Cryovial)	Central Coag (2 Green Cryovial)	Central Coag (2 Blue Cryovial)	None	None
Store -80 C				2 Amber Cryovial		3 Red Cryovial	2 Green Cryovial	2 Blue Cryovial	6 Lavender Cryovial	7 Red Cryovial

proto-5a;research

Second, fibrin fragments not pelleted with centrifugation can clog up analysis equipment, leading to errors and equipment failures.

An overall schema of sample processing is shown in figure 2.

B. Blood Collection Trays and Tubes

1. Blood Collection Tray

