In accordance with OSHA regulations on blood borne pathogens (see appendix for the complete OSHA regulations), the following laboratory safety protocol for field-center laboratories is recommended: Use of non-permeable lab coats, Latex gloves, and face shields when handling any blood in any situation where splashes, spray, splatter, or droplets of blood may be generated and eye, nose, mouth contamination can be reasonably anticipated. Follow universal precautions when handling any blood products. Contaminated needles and sharps shall be immediately placed in a puncture-resistant, leak-proof container. Never re-cap or break needles. Hepatitis B vaccine should be offered to all technicians handling blood.

2. Phlebotomy area:

The blood drawing area should take place in an isolated room or participants should be separated by room dividers. The room should be equipped with all the necessary blood drawing supplies. A separate counter or work cart should be equipped with all the materials and vials that are used for blood handling and processing. The centrifuge, refrigerator, and freezer should be near by.

3. Participant preparation:

Informed consent must be obtained before drawing blood. This procedure is followed to ensure that the subjects understand the purpose of blood drawing and the possible complications of venipuncture. A standard informed consent has been prepared for

this study. With regard to laboratory procedures, the consent statement informs study subjects that there is a small risk of bruising at the spot on the arm where the blood is taken and that about 2 tablespoons of blood are drawn. The consent statement also informs study subjects that they will be contacted if clinically important test results are abnormal.

4. Participant phlebotomy question:

Minimal fasting time required for testing is 8 hours (optimum is 12 hours), and all samples for endpoint package should be collected between 6-10 a.m. Record the time of last food and the time of blood drawing. If the participant is not fasting, the blood sample will not be drawn and the subject should be rescheduled for phlebotomy within the next three days. Similarly, if the collection time is outside the 6-10 a.m. period, the subject should be rescheduled for phlebotomy.

5. General:

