The red stopper tube #1 (6 ml) with serum separator is placed on a rack at room temperature; the purple stopper tube #2 is mixed for 30 seconds and placed on a rack at room temperature. These tubes are submitted to the field center's chemistry and hematology laboratories. The buffy-coat aliquot is obtained from 10 ml EDTA tube #3 at baseline, after centrifugation at R.T. for 10 minutes at 3000 x g. After the plasma is removed, using an MLA pipette, carefully suction off the white cell layer. Try not to disturb the red cells. The buffy coat is aliquoted into three amber vials. The second red stopper serum tube (6 ml) with serum separator is also allowed to clot at room temperature for 30 minutes and then centrifuged x 3000 g for 10 minutes. The tube is then submitted to the field center's lipid laboratory for fasting lipid profile; it should be refrigerated if not delivered to the laboratory within three hours of phlebotomy. Alternatively, 4-0.5 ml aliquots can be frozen at -80°C prior to analyses at the lipid laboratory.

C. Immediate Processing of Endpoint Samples

Upon reaching the blood processing station, remove the blood tube drawing rack and ice bath containing tube from the blood collection tray. The rack should contain three tubes: #1, #2, #3. The ice bath should contain two tubes: #4, #5. All tubes should be processed within 20 minutes of phlebotomy. The corresponding aliquot racks (two per patient) should be ready. Rack #1 (with color codes red, blue, and lavender) should be placed in an ice bath. Rack #2 (with color code green) remains at room temperature.

D. Centrifugation

Tubes #1, #2, #4, and #5 are centrifuged at 4°C for 10-20 minutes at 3,000 g. The centrifuge may need to be precooled to 4°C. 4.5 ml and 7 ml balance tubes are required for tubes #4 and #5. Simultaneously, tube #3 is centrifuged at room temperature for 10-20 minutes at 3,000 g. A 4.5-ml balance tube is required. Once centrifuged, the maximum time allowed before aliquoting is 10 minutes. While these tubes are spinning, the blood collection tray can be restocked with tube rack and blood collection tubes, ice, and forms for the next participant. Recheck labels on the two aliquot racks. Perform any necessary clean-up.

E. Aliquots

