Frozen aliquots and racks are packaged with pre-labeled freezer box. One box contains the aliquots from a single endpoint series on each patient (28 aliquots per total). The boxes containing aliquots are stored at -80°C freezer by date. The copy of the Phlebotomy Processing Form is kept in a file to be included with the shipment of samples. Restock blood collection tray with samples. Label with next day's participants. Blood draw tubes, aliquots, forms. Arrange draw tubes and aliquots in their proper racks. Wipe down all work areas with 10% Clorox solution.

I. Summary of Processing Time Limitations

On blood drawn prior to processing:

- 1) Serum 9.5 ml - 40 minutes;
- 2) Serum 9.5 ml - 40 minutes;
- 3) Citrate 4.5 ml - room temperature - 30 minutes;
- 4) Citrate 4.5 ml - 4°C - 30 minutes;
- 5) EDTA 7.0 ml - 4°C - 30 minutes;

Once centrifuged, maximum time before aliquoting is 10 minutes; after aliquoting all samples, freeze within 10 minutes.

J. Sample Processing Checklist

Pipette: MLA 2,000
Pipette: MLA 1,000
Pipette: MLA 500
Pipette tips
Pasteur pipette with bulbs
Ice bath/ice
Latex gloves
Lab mat

Kimwipes
Biohazard waste bags
Clorox (10% in wash bottle)
Pen/pencils
Study participant aliquot racks (2) with prelabeled aliquots
Phlebotomy Processing Form (page 1 completed)
Freezer
Refrigerator
Centrifuges -- room temperature and 4°C
Balance tube
Thermometer
Zip-lock bag
Lab coats, gloves, face shields

IV. SHIPPING THE BLOOD SAMPLES

A. General

Blood samples are stored at the field centers at -80°C and shipped to the various laboratories according to the schedule in Figure 3.

B. Methods

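### The venipuncture step accepts endpoint draws from 6 a.m. although the protocol says PAI-1 requires 7-10 a.m., and draw-to-processing limits for the endpoint tubes also conflict

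*Protocol*

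**What the plan says.** **Endpoint status.** Section 1.0.3: "The primary hemostatic endpoints will be plasma levels of fibrinogen, Factor VII and Plasminogen Activator Inhibitor I (PAI-1").

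**Draw window.** Three places in Chapter 8 set it:

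- I.C.8, the rationale for PAI-1: "PAI-1 levels appear to have a diurnal cycle, requiring the collection of samples between 7 and 10 a.m".
- II.A, the blood collection overview: "Each endpoint package should be collected after an 8-hour fast with sample collection occurring between 7-10 a.m".
- II.B.7.d.4, within the venipuncture procedure: "all samples for endpoint package should be collected between 6-10 a.m". The same paragraph makes this window the rescheduling trigger: "if the collection time is outside the 6-10 a.m. period, the subject should be rescheduled for phlebotomy". It also has staff record the time of the draw.

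**Time to processing.** Three places in Chapter 8 set it:

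- III.C, immediate processing of endpoint samples: "All tubes should be processed within 20 minutes of phlebotomy".
- Figure 2: "Stage 1 Centrifugation (0-20 min").
- III.I, the summary of time limits: "Citrate 4.5 ml - room temperature - 30 minutes". It gives the same 30 minutes for the 4°C citrate tube and the EDTA tube, and 40 minutes for each of the two serum tubes.

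**The concern.** The protocol gives a biological reason for a 7 a.m. start and then applies a 6 a.m. start at the step where a draw is accepted or sent away. Samples that the rationale excludes can enter the PAI-1 data without counting as a deviation.

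Each participant eats all three diets and gives four endpoint samples on each, so the diet comparison is made within person. If PAI-1 changes over the morning, a wider window lets more clock-time variation into that comparison. Section VI.E.3 already puts the PAI-1 assay CV at about 9%.

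The processing limits raise a similar problem. Four centers prepare plasma for a single central coagulation laboratory. One center could work to 20 minutes and another to 30, each with support in the manual. Section VI.E.2 asks for Factor VII plasma to be spun as soon as possible, so delay before centrifugation is something the protocol itself treats as relevant.

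**Working it through.** The protocol has no figure of its own to reproduce here. The check is a comparison of its statements, with simple differences.

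**Draw window**

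- II.B.7.d.4: 10 − 6 = 4 hours.
- I.C.8 and II.A: 10 − 7 = 3 hours.
- Disputed time: 4 − 3 = 1 hour (6-7 a.m.), which is 1/4 = 25% of the operative window.

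Three example draw times show where the rules part:

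| Draw time | II.B.7.d.4 | I.C.8 and II.A |
|---|---|---|
| 6:30 a.m. | accepted | outside |
| 7:30 a.m. | accepted | inside |
| 10:30 a.m. | rescheduled | outside |

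Only the 6-7 a.m. hour is affected. The wider window appears twice in II.B.7.d.4, once as the collection rule and once as the trigger for rescheduling, so a single-character slip is unlikely.

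The rule screens every endpoint draw. With four draws on each of three diets there are 4 × 3 = 12 per participant. For the 96 participants in the assumed design of Chapter 2, Table 1, that is 96 × 12 = 1,152 draws. The documents do not say how many would fall at 6-7 a.m., and the 25% above is a share of the window, not of the draws.

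**Time to processing**

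| Endpoint tube | Use | III.C and Figure 2 | III.I | Difference |
|---|---|---|---|---|
| #1, #2 serum | lipids, apoproteins, stored aliquots | 20 min | 40 min | +20 min (40/20 = 2 times) |
| #3 citrate, room temperature | Factor VII | 20 min | 30 min | +10 min (30/20 = 1.5 times) |
| #4 citrate, 4°C | fibrinogen, PAI-1 | 20 min | 30 min | +10 min (1.5 times) |
| #5 EDTA, 4°C | ancillary studies | 20 min | 30 min | +10 min (1.5 times) |

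The list in III.I matches the five endpoint tubes, not the four baseline tubes. Clotting time does not explain the 40 minutes for serum. Section II.B.4 says the endpoint serum tubes contain thrombin and clot in 5 minutes, while the 30-40 minute clotting time in II.B.3 belongs to a baseline tube.

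**Effect on PAI-1**

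Turning the extra hour into added variance would need three things: the change in PAI-1 per hour of the morning, the spread of draw times within a participant, and the within-person biological variation of PAI-1. The protocol gives none of them. The table of biologic plus analytical SDs in VII.B covers cholesterol, triglyceride, HDL cholesterol, apo A-1 and apo B-100, but not PAI-1. The direction is clear if the stated diurnal cycle holds; the size is not computable.

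**The case against.** **The conflict is small and traceable.** It concerns one hour at one edge, and the documents tie clock time to one analyte among ten primary endpoints. II.A is also an instruction, technicians must review the manual and pass examinations, and the recorded draw time lets early samples be found afterwards. All of this stands and limits the importance of the point. It does not settle which window applies. A technician who has read the whole manual has read both, and the rescheduling rule names only the wider one. Recording the time identifies an early sample but does not prevent it.

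**The two processing limits may be a target and an outer limit.** III.C can be read as the working aim and III.I as the ceiling. That is possible, but neither section says so, and Figure 2 repeats the shorter figure without qualification. No harm to an endpoint has been shown, so this part is a matter of consistency.

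**Stronger readings that a reader might infer.**

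- *That draw hour could bias the diet comparison*, for example if schedules change between feeding periods. The documents do not support this. Participants are randomized and assigned a diet sequence (5.2), and the food sampling plans show all three diets in use within each period. A change of hour between periods would therefore be spread over the diets. Coordinators, laboratory technicians and participants are to be masked (4.4, 5.4), which makes diet-dependent scheduling unlikely. Added noise is the most that can be claimed.
- *That the loss of precision in PAI-1 can be put as a percentage.* This would need an assumed hourly slope and independent draw times spread evenly over the window. Setting clock time against assay error alone would also leave out biological variation and so overstate its share.
- *That each participant must be drawn at a fixed hour.* No passage promises this. The protocol's chosen control is a morning window, and even 7-10 a.m. allows a three-hour spread.

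**Conclusion.** The point holds as an internal contradiction that changes which samples are accepted for a primary hemostatic endpoint. Draws at 6-7 a.m., one of the four hours allowed at the operative step, are accepted against the protocol's own PAI-1 requirement. The consequence is avoidable clock-time noise of unknown size, and it rests on the protocol's statement that PAI-1 appears to have a diurnal cycle. No bias in the diet contrast is shown.

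The processing limits are also inconsistent, by 10 minutes for the citrate and EDTA tubes and 20 minutes for serum. The affected tubes include those for all three primary hemostatic endpoints. The documents do not show what the extra minutes do to any result.

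The correction should be made because it is specific and almost free, not because a large effect has been demonstrated.

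**What to change.** 1. In Chapter 8, II.B.7.d.4, change both the collection sentence and the rescheduling sentence to 7-10 a.m., the window that I.C.8 and II.A already state.
2. Use the recorded draw time to flag any endpoint sample taken outside 7-10 a.m.
3. Reconcile III.C, Figure 2 and III.I to one draw-to-centrifugation limit for each tube type. If a target and an outer limit are both intended, label them as such. The laboratories should choose the values.
4. Optional: try to keep each participant's draw hour similar across the three feeding periods. Section 3.6.3.3 already asks for consistent appointment times for blood pressure, for the same reason. This is a suggestion and not needed to remove the contradiction.

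The cost of items 1 to 3 is manual wording, a note to the phlebotomy and processing staff, and the loss of the 6-7 a.m. slot for participants who would prefer it. Item 4 would add a scheduling burden for students and full-time employees over an 8½-month study, which is why it stays optional.

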Analytical method is an ELISA (Enzyme Linked Immunosorbent Assay) using the Macra LPa kit manufactured by Terumo (Elkton, MD). Monoclonal antibody to Lp (a), immobilized on microtiter wells, serves as the capture antibody. Bound Lp (a) is detected using a monoclonal anti LP (a) antibody conjugated with horseradish peroxidase. The complex is detected and quantified by chromagen formation upon incubation of peroxide and o-phenylenediamine substrate. A 100 microliter aliquot of serum, stored at -80°C , is used for this assay. The antisera, calibrators, and controls are provided by Terumo (Elkton, MD) in their Macro LP (a) kit. ELISA plates are read on an automated ELISA plate reader, Dynatech model MR600 set to monitor at 492 nanomoles. A calibration curve, consisting of six ampules ranging from 0-80 mg/dL Lp (a) is run in each batch. Each calibrator is run in duplicate and averaged to generate a standard curve. Each sample is analyzed in duplicate.

Two quality control samples are included in each run. If these do not match the target value within ± 2 standard deviation, the run is repeated. The precision of LP(a) at 15 mg per deciliter on the long term (day-to-day) is 3.9% and within run is 1.4%. LP(a) of 36 mg per deciliter has a long-term precision (day-to-day) of 3.8% and within run of 1.8%. Samples of LP(a) concentrations above the highest calibrator or absorbing at over 2.0 absorbing units are diluted 1-to-1 with saline and repeated on another run.

E. Coagulation Factors

1. Fibrinogen

Fibrinogen will be measured by the clot-rate method of Clauss, using a semi-automated instrument, the ST4 from Stago. The assay will be standardized using the College of American Pathologists Standardized Reference Plasma, which the UV laboratory helped establish.

In addition to outside quality assurance programs, such as the Coagulation Program of the College of American Pathologists, quality control will be established with three control materials (normal, elevated, and low) and so-called Westgard Rule (the multi-rule Shewart QC System) will be applied. Longitudinal drift will be assessed using lyophilized

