Upon receipt at local or central laboratories, samples will be inspected upon unpacking to assure that they remained frozen in transit. Any sample showing evidence of being thawed will be noted. If transportation to the local laboratory occurs immediately upon removal from the -80°C freezer (within three hours) the sample needs to be kept frozen. Any sample that showed evidence of thawing but remained cold during transport may be analyzed for lipids and lipoproteins, but not for coagulation factors. Analysis should occur within three days of receipt of these samples. Any sample that leaked during transport will not be analyzed.

Any sample that has been identified as thawed will not be included in the data analysis if the analytical results are greater than 3SD (biologic plus analytical) from the average of the other three in that set of four.

Expected biologic plus analytical SD for triplicate analysis (Clin. Chem. 36,209, 1990)

1 SD

Cholesterol	5%
Triglyceride	13%
HDL-chol	7%
Apo A-1	10%
Apo B-100	11%

Sample identity will also be verified based on packing lists and FAXed inventory lists. Any shipment that shows a discrepancy between the packing list and the actual contents may be sent back to the originating center to correct if the discrepancy cannot be resolved by a phone call.

C. Analytical Integrity

Samples will be coded such that all samples from a single subject can be identified and grouped into three sets, from each of the three diet phases. These will be analyzed for each analyte on a single run for the analyte. If any sample of a set from the end of a single diet trial is more than 3SD (biologic plus analytical) from the average of the others, it will be reanalyzed promptly to confirm the value. It is the responsibility of the laboratory performing each test to review results on a run to run basis to identify such outliers and schedule a repeat analysis.

D. Analytical Quality Control Procedures

All analytical runs will include appropriate quality control samples to assure the validity of the run. Quality control samples will be analyzed at specific intervals with each run as specified by the manual of operation for the laboratory performing the analysis. If the quality control materials do not meet the criteria set by the laboratory's manual of operation, the run must be rejected and repeated in total.

E. Longitudinal Control Procedures

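### Over-range Lp(a) samples are repeated on another run without the participant's other samples, against the one-run rule, which adds noise to the diet contrast of participants near the assay limit

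*Protocol*

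**What the plan says.** Section 1.0.3 of the Protocol lists Lp(a) among the primary lipid and lipoprotein endpoints. Each participant eats all three diets, and Chapter 8, II.A schedules "Four endpoint packages" at the end of each, so a participant contributes 12 endpoint samples.

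Two sections of Chapter 8 say how these are assayed:

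- VII.C (Analytical Integrity) has samples coded so that "all samples from a single subject can be identified and grouped into three sets, from each of the three diet phases". It continues: "These will be analyzed for each analyte on a single run for the analyte". No analyte is exempted.
- VI.D (Lipoprotein a) describes an ELISA in which "A calibration curve, consisting of six ampules ranging from 0-80 mg/dL Lp (a) is run in each batch". It then deals with high readings: "Samples of LP(a) concentrations above the highest calibrator or absorbing at over 2.0 absorbing units" "are diluted 1-to-1 with saline and repeated on another run".

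Neither section refers to the other. VI.D does not say what happens to the participant's in-range samples when one sample goes to a repeat run.

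**The concern.** The VI.D rule acts on single samples; the VII.C rule acts on participants. If a participant's 12 values lie on both sides of the limit, following VI.D as written leaves some draws on the original run, undiluted, and others on a second run with its own calibration curve and a 1-to-1 dilution.

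VII.C does not give its reason, but the natural one is that the diet comparison is within person and a run effect shared by all of a participant's samples cancels in it. Once the samples are split, the difference between the two runs stays in that participant's contrast. Replacement also depends on the value: only high readings are measured again, while readings just under the limit stand.

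What is at stake is the precision of a primary endpoint in the participants concerned. An analysis plan could not restore the one-run comparison if the companion samples were never rerun.

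**Working it through.** The documents give no figure for this effect, so there is none to reproduce. The inputs are the precision figures in VI.D.

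**Inputs**

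- At 15 mg/dL: day-to-day CV 3.9%, within-run CV 1.4%.
- At 36 mg/dL: day-to-day CV 3.8%, within-run CV 1.8%.
- Four draws per diet (II.A); top calibrator 80 mg/dL (VI.D); 96 participants (section 2.2, Table 1).

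**Assumptions.** The day-to-day CV includes within-run error. The CVs hold near 80 mg/dL and after dilution; the documents give no precision there. The within-run CV applies to one reported result.

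**Between-run component**, b = √(day-to-day² − within-run²):

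- 15 mg/dL: √(3.9² − 1.4²) = √13.25 = 3.64%, or 0.0364 × 80 = 2.9 mg/dL at 80.
- 36 mg/dL: √(3.8² − 1.8²) = √11.20 = 3.35%, or 0.0335 × 80 = 2.7 mg/dL at 80.

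**One participant's two-diet contrast.** Each diet mean averages four draws. Let k of one diet's four draws move to one other run, and none of the other diet's. With within-run CV w,

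SD = √(2w²/4 + 2(k/4)²b²).

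Using the 36 mg/dL figures (w² = 3.24, b² = 11.20), the first term is 1.62:

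| Draws moved | Second term | SD of contrast | At 80 mg/dL |
|---|---|---|---|
| 0 | 0 | √1.62 = 1.27% | 1.0 mg/dL |
| 1 | 1.40 | √3.02 = 1.74% | 1.4 mg/dL |
| 2 | 5.60 | √7.22 = 2.69% | 2.2 mg/dL |
| 3 | 12.60 | √14.22 = 3.77% | 3.0 mg/dL |
| 4 | 22.40 | √24.02 = 4.90% | 3.9 mg/dL |

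If the 3.8% is read as pure between-run error, the SDs run from 1.85% (one draw) to 5.52% (four draws). If draws from both diets move to the same repeat run, only the difference in the numbers moved counts, and the added error shrinks or vanishes. If all 12 samples are over range and are repeated together, the contrast is protected.

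**Group mean.** The number affected is not given, so it is an assumption. Take n of 96 participants, each with all four draws of one diet moved, and independent run errors. The added SD of the mean contrast is √n × √2 × 2.68 / 96 mg/dL: 0.04 for n = 1, 0.07 for n = 3, 0.09 for n = 5 and 0.13 for n = 10. Affected participants who shared the same two runs would not have independent errors, and the addition would then be larger.

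**The case against.** VII.C can be read as governing the first analysis, not as forbidding a second. The same paragraph has outlying samples reanalyzed, and a reading above the curve has no valid value on its original run, so something must be repeated. The sections on the apoproteins, fibrinogen, Factor VII and PAI-1 also dilute and re-assay single out-of-range samples. VI.D, moreover, does not prohibit taking the rest of the set along.

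Part of this stands: a repeat is needed, and the two sections can be made compatible. It does not remove the point. The repeat in VII.C serves to confirm a value already obtained on the common run, whereas the VI.D repeat supplies the value. VI.D is also the only one of these assay sections that expressly sends the sample to another run. Permission to rerun the whole set is not an instruction to do so.

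A second objection is that analytical error is only part of the noise. VII.B lists biologic plus analytical SDs of 5% to 13% for the other lipids; none is given for Lp(a). If that range applied to each Lp(a) draw, the contrast SD would be 5 × √(2/4) = 3.5% to 13 × √(2/4) = 9.2%. The run term would raise it by about 1% to 5% with one draw moved, and by about 12% to 67% with all four moved. This stands, and is a reason to treat the point as minor.

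**Conclusion.** The point holds as a minor one. VI.D and VII.C are not reconciled, and for a participant who straddles the limit the analytical SD of a diet contrast rises from about 1.3% to between 1.7% and 4.9%, depending on how many draws move. This rests on carrying the CVs stated at 15 and 36 mg/dL up to 80 mg/dL. The documents give no Lp(a) distribution, so the number of affected participants is unknown, though probably small, and under the assumptions above the effect on the group mean is slight.

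Two stronger readings are tempting. A reader might infer that run and dilution are confounded with diet. The documents do not show this: the trigger is the measured value, not the diet; a repeat run must also have its controls within 2 SD of target; and nothing indicates that the run difference favors one diet. Selective re-measurement of high readings is a reason for care, not proof of bias. A reader might also take the roughly four-fold increase (4.90/1.27 = 3.9) as typical. It requires all four draws of one diet and none of the other's to move; with one or two draws moved the increase is 1.4-fold (1.74/1.27) to 2.1-fold (2.69/1.27).

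**What to change.** In VI.D, state that when any endpoint sample of a participant is above the highest calibrator or 2.0 absorbance units, all of that participant's endpoint samples are repeated at the same dilution on one run, and that only the results of that run are used. A reference to VII.C would make the two sections agree. Run effects then cancel, and the contrast returns to an analytical SD of about 1.3%, on the same precision assumptions.

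The cost is up to 12 repeat assays for each affected participant, and in-range results already obtained are set aside. Serum should suffice: VI.D uses a 100 microliter aliquot, the cryovials hold 0.5 ml, and Figure 3 of Chapter 8 archives 14 red-coded vials per draw. Timing is no obstacle, since Figure 3 ships the serum of all three diet phases to the Lp(a) laboratory on the same date.
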